## 10. ADVERSE EVENT REPORTING

### 10.1 Definitions

Table 5: Definitions for Adverse Events

|   |          |   |
|---|----------|---|
| Severity Definitions                         | Mild     | Awareness of signs or symptoms that do not interfere with the participant's usual activity or are transient and resolved without treatment and with no sequelae.  |
|   | Moderate | A sign or symptom, which interferes with the participant's usual activity.  |
|   | Severe   | Incapacity with inability to do work or perform usual activities (including life threatening events and fatality).  |
| Adverse Event                                | AE       | Any untoward medical occurrence in a participant participating in the trial which does not necessarily have a causal relationship with the intervention received.   |
| Related Event                                | RE       | An event which resulted from the administration of any of the research procedures.  |
| Serious Adverse Event                        | SAE      | An untoward occurrence that:
Results in death
Is life-threatening*
Requires hospitalisation or prolongation of existing hospitalisation
Results in persistent or significant disability or incapacity
Consists of a congenital anomaly/ birth defect
Or is otherwise considered medically significant by the Investigator** |
| Unexpected Event                             | UE       | The type of event that is not listed in the protocol as an expected occurrence.   |
| Related and Unexpected Serious Adverse Event | N/A      | A SAE that meets both the definition of a Related and Unexpected Event.   |

\* The term life-threatening is defined as diseases or conditions where the likelihood of death is high unless the course of the disease is interrupted.

\*\* Medical events that may not be immediately life-threatening or result in death or hospitalisation but may jeopardise the participant or may require intervention to prevent one of the other outcomes listed in the definitions above.

## **10.2 Adverse event recording – general**

The recording and reporting of AEs will be in accordance with the UK Policy Framework for Health and Social Care Research, the Principles of GCP as set out in the UK Statutory Instrument (2004/1031; and subsequent amendments) and the requirements of the HRA. Definitions for AE reporting are listed in Table 5 in Section 10.1.

It is routine practice to record AEs in the participant's medical notes and it is also recommended that this includes the documentation of the assessment of severity and seriousness and also of causality (relatedness) in relation to the intervention(s) in accordance with the protocol.

## **10.3 Adverse event reporting period**

The reporting period for AEs and Serious Adverse Events (SAEs) in TONIC will be:

- For PN related SAEs: from the day of PN until the end of the trial (90 days post-operation).
- For surgery related SAEs: from the day of surgery until the end of the trial (90 days post-operation).

The overall defined reporting period will end 90 days post-operation. After the participant has reached 90 days post-operation, sites will not be actively following up participants for SAEs.

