## **Secondary Objectives**

Secondary objectives are to:

- Assess the impact of early PN on post-operative complications up to 90 days post-operation
- Assess the impact of early PN on activities of daily living up to 90 days post-operation
- Assess the impact of early PN on muscle function with sit to stand test at hospital discharge
- Assess the impact of early PN on patient reported outcomes (gastrointestinal recovery (PRO-diGI), quality of recovery (QoR-15)) up to 90 days post-operation
- Assess the rate of SAE related to early PN up to 89 days post-operation
- Assess the impact of early PN on unplanned readmissions following discharge up to 90 days post-operation
- Assess the impact of early PN on hospital length of stay during index admission
- Assess the impact of early PN on discharge destination following index admission
- Assess the impact of early PN on participant satisfaction with treatment
- Report PN use in both arms, including duration and calories administered
- Report use of any nutritional intervention in either trial arm
- Report pathway metrics related to randomisation, line insertion, operation, and time to starting PN.

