### 6.3 Randomisation process

Randomisation should be performed pre-operatively for all participants.

Randomisation will be provided by BCTU using a secure online Electronic Data Capture (EDC) system (available at <https://bctu-redcap.bham.ac.uk/>), thereby ensuring allocation concealment. Unique log-in usernames will be provided to those who wish to use the online EDC system and who have been delegated the role of randomising participants into the trial as detailed on the TONIC Site Signature and Delegation Log. These unique log-in details must not be shared with other staff and in no circumstances should staff at sites access the system using another person's login details. The online EDC system will be available 24 hours a day, 7 days a week, apart from short periods of scheduled maintenance.

In the rare instance of the online system being unavailable, the trial office should be contacted and are available Monday to Friday, 09:00 to 17:00 UK time, except for bank holidays, government guided closures and University of Birmingham (UoB) closed days.

**Please note: to randomise a patient when the online system is unavailable, the TONIC Trial Office should be contacted directly via email or telephone using the contact details outlined at the front of the protocol.**

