### 7.1 Trial intervention(s)

Participants will be randomised to receive:

- Early PN through central venous catheter (CVC) or PICC, commencing within 48 hours of emergency laparotomy/laparoscopy, with biochemistry monitoring as per NICE Clinical Guideline 32[33]
- Standard nutritional care, which may include no support, oral nutritional supplements or nasoenteric feeding at anytime point. Clinicians can use PN in the control group, but, as per NICE guidance, not before 5 days post-surgery unless there is pressing clinical need.

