### 7.2 Trial intervention: Parenteral Nutrition

The trial intervention is intentionally pragmatic. Patients randomised to the intervention arm will receive early PN which will be administered intravenously and should be delivered either through a dedicated lumen of a central line placed at operation, or through a PICC line. These lines are inserted by anaesthetists or by specialised vascular access services, depending on local service specifications. Line access may be secured at any point from randomisation to commencement of intervention. Placement of these lines will be confirmed with a plain radiograph of the chest and is undertaken as per local processes, using aseptic techniques. Blood tests are performed prior to commencement of PN to ensure sodium, potassium, magnesium, and phosphate are in the correct range

PN is available pre-formulated from multiple suppliers in the UK. The trial does not specify or mandate the use of any particular brand; participating sites should continue to use the PN formulation routinely employed in their standard clinical practice. Sites will already have familiarity with a particular brand and will use this for the trial. PN provides carbohydrates, lipids, amino acids, vitamins, trace elements, electrolytes and water. These amounts vary according to the supplied bag. An appropriate base PN bag is selected based upon the nutrients required, particularly calories. Additional electrolytes can be added, tailored to the patient's biochemistry. The administration of PN is defined in UK guidance from NICE[26], which provides guidance on calculating calorie requirements. Sites will calculate appropriate rates of PN to be administered prior to commencement. Out of hours, this may include administering a volume defined by local out-of-hours feeding protocols, rather than a dose tailored to exact calorie requirements. At the commencement of PN, dosing is at a reduced rate to avoid metabolic consequences. This is slowly increased with ongoing monitoring of blood tests for evidence of electrolyte disturbance (e.g. abnormal sodium, potassium, phosphate, or magnesium levels). Blood tests (biochemistry including renal and liver function) are required daily for the first week of administration and

---

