| Assessment of patient treatment satisfaction Visual Analog Scale (VAS)            |           |          |                    |   |              | ✓                  | ✓                  |
| Health Resource Use Questionnaire Form  |           | ✓        |                    |   |              | ✓                  | ✓                  |
| Safety and complications   |           |          |                    |   |              |                    |                    |
| Side effects/adverse events   |           |          | ✓                  | ✓   | ✓            | ✓                  | ✓                  |
| Nutrition intervention related complications including metabolic and line-related |           |          | ✓                  | ✓   | ✓            | ✓                  | ✓                  |
| Process measures   |           |          |                    |   |              |                    |                    |
| Use and duration of PN/ other nutritional interventions                           |           |          |                    |   | ✓            | ✓                  | ✓                  |
| Time to line insertion & time to commence PN                                      |           |          |                    | ✓   |              |                    |                    |

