### **10.5.1 Serious Adverse Events not requiring reporting to the Trial Office**

Some events that meet the definition of an SAE will not require reporting to the Trials Unit on the trials dedicated SAE form or other CRFs. If any of the events outlined below in Table 6 occur during an individual's participation, from the date of surgery through to end of follow-up, reporting the event on a SAE form or on other CRFs is NOT required as these events are not considered to be critical to evaluations of the safety of the trial.

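### The reporting window for PN-related SAEs opens on the day of PN, so harm from a line placed earlier, or in a participant who never starts PN, has no such window

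*Protocol*

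**What the plan says.** Section 10.3 defines two windows and no others. The first is "For PN related SAEs: from the day of PN until the end of the trial (90 days post-operation"). The second is "For surgery related SAEs: from the day of surgery until the end of the trial (90 days post-operation"). Neither start is tied to randomisation, allocation or line insertion.

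Section 6.3 states "Randomisation should be performed pre-operatively for all participants". Section 7.2 states "Line access may be secured at any point from randomisation to commencement of intervention", with the route being either a central line sited during the operation or a PICC. Section 7.1 has PN "commencing within 48 hours of emergency laparotomy/laparoscopy".

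Section 10.5.2.2 and Table 8 list the SAEs to be collected for participants allocated to PN. The list includes PICC/CVC complications: pneumothorax and line infection, fracture, occlusion and thrombosis. Table 5 defines a related event by reference to any research procedure, not only the infusion.

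Table 4 in section 9.1 has a row "Nutrition intervention related complications including metabolic and line-related", ticked at Surgery (Day 0), during the hospital stay, at discharge, at Day 30 and at Day 90, but not at Baseline. Section 2.2.1 gives the secondary objective "Assess the rate of SAE related to early PN up to 89 days post-operation".

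**The concern.** The protocol treats line complications as harms of the PN strategy, but times their reporting window by the start of the infusion. The line has to be in place before PN can run, and some of its complications, pneumothorax being the clearest, arise at insertion. A window that opens on the day of PN can therefore miss the period in which insertion harm occurs.

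There is a second mismatch. Table 8 applies by allocation, whereas the 10.3 window applies by receipt. A participant allocated to PN who has a line placed but never starts PN has no day of PN, so the window never opens.

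What is at stake is the rate of SAEs related to early PN, which is a stated objective and part of the safety information that section 16.6 sends to the DMC. Any events left out would be harms of the intervention arm, so the error runs in one direction.

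**Working it through.** The protocol states no figure to reproduce, so the check sets the passages side by side and bounds the gap in time.

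**Step 1. Order of events.** Randomisation (pre-operative, 6.3), then line insertion (any time up to PN start, 7.2), with surgery before or after insertion, then PN within 48 hours of surgery (7.1).

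**Step 2. Coverage of line harm by timing.**

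| When the line harm occurs | PN-related window (10.3) | Surgery-related window (10.3) | Table 4 line-related row |
|---|---|---|---|
| Before the day of surgery | No | No | No tick at Baseline |
| Day of surgery up to the day before PN | No | Only if a site calls it surgery-related | Yes |
| On or after the calendar day of PN | Yes | Not needed | Yes |
| Day of surgery onward, PN never started | No window exists | Only if a site calls it surgery-related | Yes |

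The first row is outside everything. In the second and fourth rows, 10.3 and Table 4 disagree, and no passage says which governs.

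**Step 3. Length of the gap for a participant who starts PN on time.**

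Gap = wait from randomisation to surgery + time from surgery to PN.

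- Time from surgery to PN: at most 48 h (7.1).
- Wait from randomisation to surgery: not given. Section 5.2 quotes median times from admission to surgery of 10, 17 and 34 h by urgency class. As an assumed range I take 0 h to 34 h.
- Lower end: 0 + 48 = 48 h. Upper end: 34 + 48 = 82 h.

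These are the longest gaps under each assumed wait, for PN started at the 48 h limit. Three qualifications apply. The quoted times run from admission, so they overstate the wait from randomisation for a typical patient. They are medians, so some patients wait longer, and Table 1 allows days for expedited cases. The window opens on a calendar day, so insertion harm earlier on the same day as PN is inside it.

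**Step 4. Does the primary outcome recover the missed events?** Section 8.2.1 counts complications from after the operation to discharge. It can record a post-operative line complication, but not one before surgery.

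**Step 5. End of the window.** The objective in 2.2.1 runs to 89 days post-operation; 10.3 runs to 90. The two differ by one day.

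**The case against.** The strongest reply is that most line harm will be captured whatever 10.3 says. Table 8 applies by allocation, so non-starters are in scope. Table 4 collects line-related complications from Day 0, whether or not PN starts. Post-operative complications are gathered in both arms for the CCI. Section 10.5 requires every SAE to follow one of three routes. This largely stands: post-operative line events are not necessarily lost. It does not remove the conflict, because 10.3 is the section that defines the period, while 10.5 only sets the route. An event recorded as a surgical complication also need not be counted as related to PN.

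It can also be argued that the Table 4 column for the index hospital stay includes the pre-operative days, since line insertion is recorded in that column. That is possible, but the column follows Surgery (Day 0) and the table does not say so.

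A reader might draw three stronger conclusions that the text does not support:

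- That Table 4 adds a third start date. It does not: Day 0 is the day-of-surgery start already in 10.3. Section 10.5.1 uses the same start ("from the date of surgery through to end of follow-up"), but only for exempt SAEs.
- That the pilot amber band for delivery (70-99% in the PN arm, Table 3) counts the participants with no window. It does not: that criterion concerns starting within 48 hours, so it mixes late starters, whose window does open, with never-starters, and includes people who may never have had a line.
- That the SAE rate will be too low. That follows only if sites apply 10.3 in preference to Tables 4 and 8.

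**Conclusion.** The gap is real but narrow. Under 10.3 as written, line harm before the day of PN, and line harm in allocated participants who never start PN, has no PN-related window. For events from the day of surgery onward this is a conflict with Table 4, and many would probably still be recorded. For a line inserted before the day of surgery, the harm lies outside both 10.3 windows and the Day 0 tick.

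The rate of SAEs related to early PN may therefore be understated. The amount cannot be estimated, because the protocol does not give the share of lines placed before surgery, the number of non-starters with a line, or the rate of insertion complications. The conclusion assumes that sites take 10.3 literally and that the hospital-stay column of Table 4 begins at surgery. The primary analysis is not affected.

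**What to change.** In section 10.3, start the window for PN-related SAEs, stated to include PICC/CVC complications, at randomisation for all participants allocated to PN, whether or not PN is started. An acceptable alternative is the earlier of line insertion and first PN. Leave the surgery-related window as it is. Moving every SAE in both arms to randomisation would widen a scheme that sections 10.4 and 10.5.2.2 deliberately keep targeted, and the gap does not require it.

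Extend the line-related row of Table 4 back to the same start. Reconcile the 89 days in section 2.2.1 with the 90 days in section 10.3.

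The cost is an amendment to wording and a few additional line-related SAE entries. No visit or procedure is added.

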## **10.4 Adverse events reporting in TONIC**

Participants that meet the eligibility criteria for the TONIC Trial may experience numerous AEs. As these events are well characterised, it is highly unlikely that these AEs will reveal any new safety information relating to the trial intervention, PN. Due to this, events that meet the definition of an AE but not an SAE (see Table 5) will NOT be required to be reported to the trial team, these AEs should however be recorded as per local practice.

## **10.5 Serious Adverse Events reporting in TONIC**

It is recognised that the frequency of SAEs in this participant population may be high. Many of these SAEs will be anticipated due to the potential of either the operation or PN undertaken by the participant. We have therefore outlined anticipated SAEs that do not require reporting and anticipated SAEs that do not require expedited reporting.

---

For all SAEs, the PI or delegate must do one of the following:

1. **Record safety reporting-exempt SAEs** in the medical notes but **not report** them to the trials office as per Section 10.5.1.
2. **Report SAEs to the trial office in a non-expedited manner.** This can only be done for the pre-defined subset of SAEs as per Section 10.5.2.
3. **Report SAEs to the trial office in an expedited manner** (within 24 hours of the site research team becoming aware of the event). All SAEs not covered by the above 2 categories must be reported as per Section 10.5.3.

**Note:** when an SAE occurs at the same hospital at which the participant is receiving trial intervention or is being followed up for trial purposes, processes must be in place to make the trial team at the hospital aware of any SAEs, regardless of which department first becomes aware of the event, in an expedited manner.

### **10.5.1 Serious Adverse Events not requiring reporting to the Trial Office**

Some events that meet the definition of an SAE will not require reporting to the Trials Unit on the trials dedicated SAE form or other CRFs. If any of the events outlined below in Table 6 occur during an individual's participation, from the date of surgery through to end of follow-up, reporting the event on a SAE form or on other CRFs is NOT required as these events are not considered to be critical to evaluations of the safety of the trial.

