### **1.2.4 Justification of choice of primary outcome**

The primary outcome was selected following focus groups with patients and clinicians, and a review of the literature[27]. The outcome most likely to be affected in the short term by the intervention is post-surgical complications, based upon clinical experience, supporting data from the national audit of small bowel obstruction[28], and the 2019 Schuetz trial[13]. This will be measured using the Comprehensive Complication Index (CCI)[29].

The CCI is based on the conventional Clavien-Dindo classification (CDC) which has been widely used in surgical research[29]. The CCI is the mathematical summation of complications graded using the conventional CDC and takes into account the number and severity of each complication to obtain a value from 0 (no complications) to 100 (death). As all post-operative complications are included, it is more sensitive than other surgical morbidity endpoints.

This score allows for repeated complications during an admission, and not simply the worst complication. This means that several minor complications can give a higher score than a single bad complication. The nuance afforded by this score increases the likelihood of detecting differences between groups.

The day of discharge has been selected as the time to assess for in-hospital complications (primary outcome). This is a plausible timepoint to assess the effect of the intervention, and will allow us to accurately collect data on complications. The common complications where we anticipate the effect of the intervention are in wound healing and infection, including both wound and respiratory infections. Complications occurring after discharge are temporally distant from the intervention and therefore less attributable to this. Ascertainment of complications at 30 and 90 days is also increasingly challenging, and so data might be unreliable.

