#### Comprehensive Complication Index

The CCI is based on the conventional CDC which has been widely used in surgical research[36, 37]. The CCI is the mathematical summation of complications graded using the conventional CDC and takes into account the number and severity of each complication to obtain a value from 0 (no complications) to 100 (death). As all post-operative complications are included it is more sensitive than other surgical morbidity endpoints[38]. There is an online tool available to calculate the CCI at [CCICalculator.com](http://CCICalculator.com).

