**Table 6: SAEs that do not require reporting**

| Expected SAE   | Process                        |
|--|--------------------------------|
| Pre-planned hospitalisation  |                                |
| SAEs related to pre-existing condition                                       |                                |
| SAEs that are related to symptoms or progression of the participants disease | Document in medical notes only |

All events which meet the definition of serious must be recorded in the participant notes, including the causality and severity, throughout the participant's time on trial, including follow-up, but for trial purposes these events do not require reporting on the SAE Form. Such events are "safety reporting exempt".

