**Table 9: SAE that require expedited reporting**

| Expected SAE   | Process  |
|--|--|
| Death  |  |
| Line infection – if it leads to systemic sepsis, requires escalation to HDU/ITU, or is considered medically significant by the investigator. | Report on SAE Form and provide to the TONIC Trial Office within 24 hours of becoming aware of the event. |

Any other SAEs that are related and unexpected would require expedited reporting to the trial office.

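### Section 10.5.1 waives CRF entry for disease-related SAEs, some of which may also be complications that the primary outcome must count, and the SAE routes conflict in two other places

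*Protocol*

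**What the plan says.** **The exemption.** Protocol Section 10.5.1 refers twice to CRFs other than the SAE form when it lifts the reporting requirement. The second time it says that "reporting the event on a SAE form or on other CRFs is NOT required as these events are not considered to be critical", and the sentence ends by tying this to evaluating the safety of the trial. The waiver runs from surgery to the end of follow-up. Table 6 lists the exempt events: pre-planned hospitalisation, SAEs related to a pre-existing condition, and "SAEs that are related to symptoms or progression of the participants disease". Its process column sends them to the medical notes only. The paragraph under the table is narrower: "for trial purposes these events do not require reporting on the SAE Form".

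**The primary outcome.** On the CCI, Section 8.2.1 says: "As all post-operative complications are included it is more sensitive than other surgical morbidity endpoints". Section 1.2.4 adds that "several minor complications can give a higher score than a single bad complication". Section 14.2.1 builds the score from all recorded complications with a Clavien-Dindo grade, and Table 15 scores death as 100. Section 9 (At discharge) has complications captured from clinical notes and the clinical team, then graded by the research team with the local PI. Table 4 has a CCI row, including mortality, at discharge, day 30 and day 90.

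**The routes.** Section 10.5 gives three routes and requires one of them for every SAE: notes only and not reported, non-expedited, or expedited. It closes with "All SAEs not covered by the above 2 categories must be reported as per Section 10.5.3". Table 9 in Section 10.5.3 lists death and certain line infections, followed by: "Any other SAEs that are related and unexpected would require expedited reporting to the trial office".

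**The concern.** The safety section and the outcome section draw on the same events, and no sentence separates them. A site following Section 10.5.1 literally may classify a serious post-operative event as disease-related, write it in the notes and enter nothing on any CRF. If that event is also a complication, the CCI needs it.

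The boundary is not clear-cut in this population. Section 1.1 gives intra-abdominal sepsis, perforation, obstruction and ischaemia as the reasons for surgery. Continuing sepsis or further ischaemia afterwards can reasonably be called either disease progression or a complication.

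Section 6.6 says that clinicians and outcome assessors are not blinded, so the choice is made with the allocation known. If it were made differently in the two arms, ascertainment of the primary outcome would differ by arm. Because the waiver lasts until the end of follow-up, the same ambiguity reaches the 30- and 90-day CCI.

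**Working it through.** The point rests on comparing texts.

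**1. Section 10.5.1 against itself.** The opening paragraph lifts reporting on the SAE form and on other CRFs. The paragraph under Table 6 lifts it on the SAE form only. The two scopes differ within one section.

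**2. Section 10.5.1 against the CCI.** Take a serious, disease-related event after surgery and before discharge.
- Section 10.5, first route: record in the notes, do not report to the trials office.
- Section 10.5.1 and Table 6: no CRF required, notes only.
- Sections 8.2.1, 9 and 14.2.1 and Table 4: if it is a post-operative complication, it is captured, graded and counted.

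Nothing says which instruction prevails. By contrast, Section 10.5.2 says explicitly that its non-expedited events still go on the relevant CRFs. Section 10.5.1 has no such sentence.

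**3. Does Table 7 close the gap?** Table 7 sends 16 named events to trial CRFs for all participants, including pneumonia, intra-abdominal collection, anastomotic leak and unplanned ICU admission. It covers much of the expected morbidity. It does not name sepsis, ischaemia, re-perforation or recurrent obstruction. A named event can also fit both tables, for example atrial fibrillation in a participant with earlier heart disease. No precedence rule is given.

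**4. A disease-related death.** By cause it falls under Table 6 (notes only). By outcome it falls under Table 9 (SAE form within 24 hours). Section 10.5 requires one route and does not say which table governs.

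**5. An SAE that is unrelated to the intervention or operation and is in none of Tables 6 to 9.**
- Section 10.5: expedited, because it lies outside the first two categories.
- Section 10.5.3: not expedited, because beyond the listed events only related and unexpected SAEs qualify.

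The two sections give opposite instructions.

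**6. Sample size.** Inputs from Section 14.1: difference 6, SD 27, two-sided 5% significance, 90% power, 5% attrition; 1:1 allocation from Section 3.1.
- n per arm = 2 × (1.960 + 1.282)² × 27² / 6² = 2 × 10.51 × 20.25 ≈ 425.6, rounded up to 426.
- 426 / 0.95 = 448.4, rounded up to 449 per arm, 898 in total.

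This reproduces the protocol's figure, and the wording change does not alter it. The protocol gives no rate at which complications would be misfiled as disease and no expected difference in that rate between arms, so no bias or loss of power can be derived.

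**The case against.** The best defence is that Section 10 concerns safety reporting and the CCI does not depend on it. The waiver says that reporting is not required; it does not forbid entry on outcome forms. Its sentence ends with safety evaluation, and the text under Table 6 calls these events exempt from safety reporting. Section 9 collects complications from the notes and the clinical team, and Table 4 keeps the CCI row separate from the adverse-event row. An event kept only in the notes is therefore still in the CCI's source. Unblinded grading by site staff is disclosed and would exist whatever Section 10 said. Most of this stands, and it is why the consequence is a risk and not a demonstrated loss.

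It does not remove the conflict. The waiver names other CRFs, which goes beyond the SAE form, and no sentence protects the CCI forms from it.

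A reader might infer three stronger things that the protocol does not support:
- **Minor complications are lost.** Section 10.4 says that non-serious AEs "will NOT be required to be reported to the trial team". That is a safety-reporting rule and does not mention CRFs. Minor complications still reach the CCI through Section 9. Only a cross-reference is missing.
- **Deaths go unrecorded.** Table 9 requires an SAE form, Table 4 lists mortality with the CCI, and Table 13 requires a trial exit form on death. What remains is the double classification.
- **The primary estimate is biased by a known amount.** Any figure would rest wholly on assumed rates of omission and assumed points per event.

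**Conclusion.** The point holds as a conflict between stated rules. Section 10.5.1 waives CRF entry more widely than its own later paragraph does and, read literally, conflicts with the collection of every post-operative complication for the primary outcome. Two further conflicts stand: Table 6 against Table 9 on a disease-related death, and Section 10.5 against Section 10.5.3 on unlisted, unrelated SAEs. These two concern safety reporting and do not show loss of outcome data.

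The effect on the CCI cannot be sized from the protocol. It depends on how often sites would treat an ambiguous event as disease progression, whether they would then also leave it off the complications form, and whether that differs by arm. The conclusion assumes only that some serious post-operative events can fairly be read both ways, which the indications in Section 1.1 make plausible. The wording should be corrected because it bears on primary-outcome ascertainment in an unblinded trial and the correction is small.

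**What to change.** 1. In Section 10.5.1, delete both references to other CRFs, so that the exemption covers the SAE form only and agrees with the paragraph under Table 6. Bring the Table 6 process column and the first route in Section 10.5 into line.
2. Add to Section 10.5.1, with a cross-reference in Section 10.4, a sentence such as: the safety-reporting exemptions do not affect the CCI; every post-operative complication of any Clavien-Dindo grade, and every death, is entered on the complications CRF in both arms.
3. Reconcile Table 6 with Table 9 by stating which governs a disease-related death.
4. Reconcile Section 10.5 with Section 10.5.3, so that both give the same rule for SAEs that appear in no table.

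The cost is protocol wording and a short addition to site training. No data item is needed beyond those the CCI already requires, and the sample size stays at 898.
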